#### 4.0 Study Calendar

##### 4.1 Test Schedule for Breast Cancer

Tests and procedures			Active Treatment									End of Treatment	Post-Treatment
	$\leq 28$ days prior to registration	$\leq 14$ days prior to registration	Pre-Tx biopsy	Cycle 1 binimetinib alone	Cycles 2-3 with pembrolizumab		Cycles 4-8	Cycle 9	Cycle 10 and beyond	At time of disease progression	Safety follow up: 30 days post-discontinuation		
					Prior to C2 D1	Prior to C3 D1	Prior to Day 1	Prior to Day 1					
Window					$\pm 3$ days	$\pm 3$ days	$\pm 3$ days	$\pm 3$ days	$\pm 3$ days	$\pm 7$ days		$\pm 7$ days	
Clinical Procedures													
History and exam  , vital signs (temp, BP, heart rate), weight, ECOG PS	X				X	X	X	X	X	X		X	
Height	X												
Concomitant medications	X				X	X	X	X	X			X	
Pregnancy test 		X 											
Hematology: CBC/diff with PLT		X			X	X	X	X	X			X	
Chemistry Panel 		X			X	X	X	X	X			X	
CA15-3		X			X	X	X	X	X			X	
Creatine Kinase (CK/CPK), troponin T 4,R		X			X	X	X	X	X			X	
Urinalysis		X			X	X	X	X	X			X	
Coagulation INR (PT), PTT		X											
Total T3, Free T4, TSH R		X			X	X	X	X	X			X	
Tumor measurement by CT or MRI 	X						X						
Bone scan (only if clinically indicated)	X												

\*Retreatment Phase-Patients entering the study for retreatment will follow the test and procedures as indicated in the study calendar for Cycle 2 and beyond. Labs and blood forms are not required to be entered into RAVE during the Retreatment Phase.

 All tests and procedures are clinically indicated, unless noted with an R to indicate funding by research

 For women of childbearing potential only: Serum  $\beta$ HCG must be done  $\leq 7$  days prior to registration, and if necessary, again  $\leq 72$  hours prior to Cycle 1, Day 1

 AST (SGOT), ALT (SGPT), alkaline phosphatase, total bilirubin (direct if TBili is elevated), BUN, creatinine with calculated creatinine clearance, albumin, total protein, uric acid, bicarbonate, calcium, chloride, glucose, LDH, magnesium, phosphorus, potassium, sodium

 Follow up for total creatine kinase (CK/CPK)  $\geq 3$  X ULN will include weekly assessment of isoenzymes and myoglobin in blood/or urine, and troponin T as applicable

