 Every 12-16 weeks after Cycle 4 during active treatment (per the treating physician's discretion). Same method should be used throughout the study. Note: PET/CT is not allowed as CT portion of PET/CT is not adequate for RECIST.

Tests and procedures			Active Treatment								End of Treatment	Post-Treatment
	$\leq 28$ days prior to registration	$\leq 14$ days prior to registration	Pre-Tx biopsy	Cycle 1 binimetinib alone	Cycles 2-3 with pembro		Cycles 4-8	Cycle 9	Cycle 10 and beyond	At time of disease progression	Safety follow up: 30 days post-discontinuation	
					Prior to C2 D1	Prior to C3 D1	Prior to Day 1	Prior to Day 1				
Window					$\pm 3$ days	$\pm 3$ days	$\pm 3$ days	$\pm 3$ days	$\pm 3$ days	$\pm 7$ days	$\pm 7$ days	
ECG, 12 lead, triplicate R	X					X						
Echocardiogram (ECHO)  – limited, LVEF only	X				X 		X 		X 		X	
Full ophthalmic evaluation 	X					X 	X 		X 		X	
Adverse event assessment	X			X	X	X	X	X	X	X	X	
Research Blood and Tissue- Analysis												
Blood for correlative research 8,R (See Section 14.0)			X		X	X		X			X	
Mandatory tissue sample (see Section 17.0) 9,10,R			X									
Optional follow up tissue sample(see Section 17.0) 11,R					X					X		

 Echocardiogram will be performed at baseline, on Cycle 2 Day 1, and Cycle 5 Day 1, then every 12 weeks to determine cardiac ejection fraction in patients who continue on binimetinib. Follow-up echocardiogram is not required in patients who discontinue binimetinib.

 Full ophthalmic examination will be performed at baseline, at Cycle 3 Day 1  $\pm 7$  days, and then every 12 weeks  $\pm 7$  days in patients who continue on binimetinib. Follow-up ophthalmic examination is not required in patients who discontinue binimetinib. Full ophthalmic examination includes best corrected visual acuity, slit lamp examination, intraocular pressure, dilated fundoscopy and Ocular Coherence Tomography (OCT). Examination of the retina is required, especially to identify findings associated with serous retinopathy and RVO. For patients with clinical suspicion of retinal abnormalities of any grade (e.g., serous retinopathy, RVO, photopsia, metamorphopsia, impairment of visual acuity), these additional assessments should be mandatory:

- For non-vascular abnormalities: spectral domain OCT recommended

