### 11.1 Schedule of Evaluations

For the purposes of this study, patients should be reevaluated every 6 weeks. In addition to a baseline scan, confirmatory scans should also be obtained 4 weeks following initial documentation of objective response.

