#### **11.33 Measurement at Follow-up Evaluation:**

A subsequent scan must be obtained a minimum of 4 weeks following initial documentation of an objective status of either complete response (irCR) or partial response (irPR).

In the case of stable disease (SD), follow-up measurements must have met the SD criteria at least once after study entry at a minimum interval of 6 weeks (see Section 11.44).

NOTE: Once patient has had SD for  $\geq 6$  months, scanning can be reduced to every 3 months.

The cytological confirmation of the neoplastic origin of any effusion that appears or worsens during treatment when the measurable tumor has met criteria for response or stable disease is mandatory to differentiate between response or stable disease (an effusion may be a side effect of the treatment) and progressive disease.

- Cytologic and histologic techniques can be used to differentiate between PR and CR in rare cases (e.g., residual lesions in tumor types such as germ cell tumors, where known residual benign tumors can remain.)

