**11.43 irRECIST Response Criteria**

11.431 All target lesions and target lymph nodes followed by CT/MRI/PET-CT/Chest X-ray/physical examination must be measured on re-evaluation at evaluation times specified in Section 11.1. Specifically, a change in objective status to either irPR or irCR cannot be done without re-measuring target lesions and target lymph nodes.

**Note:** Non-target lesions and non-target lymph nodes should be evaluated at each assessment, especially in the case of first response or confirmation of response. In selected circumstances, certain non-target organs may be evaluated less frequently. For example, bone scans may need to be repeated only when complete response is identified in target disease or when progression in bone is suspected.

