**11.44 RECIST 1.1 Response Criteria**

11.441 All target lesions and target lymph nodes followed by CT/MRI/PET-CT/Chest X-ray/physical examination must be measured on re-

evaluation at evaluation times specified in Section 11.1. Specifically, a change in objective status to either a PR or CR cannot be done without re-measuring target lesions and target lymph nodes.

**Note:** Non-target lesions and non-target lymph nodes should be evaluated at each assessment, especially in the case of first response or confirmation of response. In selected circumstances, certain non-target organs may be evaluated less frequently. For example, bone scans may need to be repeated only when complete response is identified in target disease or when progression in bone is suspected.

11.442 Evaluation of Target Lesions

Complete Response (CR): All of the following must be true:

- a. Disappearance of all target lesions.
- b. Each target lymph node must have reduction in short axis to  $<1.0$  cm.

Partial Response (PR): At least a 30% decrease in PBSD (sum of the longest diameter for all target lesions plus the sum of the short axis of all the target lymph nodes at current evaluation) taking as reference the BSD (see Section 11.41).

Progression (PD): At least one of the following must be true:

- c. At least one new malignant lesion, which also includes any lymph node that was normal at baseline ( $<1.0$  cm short axis) and increased to  $\geq1.0$  cm short axis during follow-up.
- d. At least a 20% increase in PBSD (sum of the longest diameter for all target lesions plus the sum of the short axis of all the target lymph nodes at current evaluation) taking as reference the MSD (Section 11.41). In addition, the PBSD must also demonstrate an absolute increase of at least 0.5 cm from the MSD.
- e. See Section 11.32 for details in regards to the requirements for PD via FDG-PET imaging.

Stable Disease (SD): Neither sufficient shrinkage to qualify for PR, nor sufficient increase to qualify for PD taking as reference the MSD.

11.443 Evaluation of Non-Target Lesions & Non-target Lymph Nodes

Complete Response (CR): All of the following must be true:

- a. Disappearance of all non-target lesions.
- b. Each non-target lymph node must have a reduction in short axis to  $<1.0$  cm.

Non-CR/Non-PD: Persistence of one or more non-target lesions or non-target lymph nodes.

Progression (PD): At least one of the following must be true:

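### The study calendar sets tumour scans every 12-16 weeks after Cycle 4 at physician discretion; Section 11.1, which governs response measurement, says every 6 weeks and gives no starting point

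*Combined protocol and SAP*

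**What the plan says.** Section 4.1, calendar: the row "Tumor measurement by CT or MRI" carries footnote 5, which sets imaging "Every 12-16 weeks after Cycle 4 during active treatment (per the treating physician"'s discretion). As the table reads, the row is marked at baseline and under Cycles 4-8. The point rests on the footnote, not on the position of the marks.

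Section 11.1: "For the purposes of this study, patients should be reevaluated every 6 weeks", plus a confirmatory scan 4 weeks after a first response. It does not say whether the 6 weeks run from registration, Cycle 1 Day 1 (C1D1) or Cycle 2 Day 1 (C2D1).

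Section 11.431 (irRECIST): target lesions and nodes "must be measured on re-evaluation at evaluation times specified in Section 11.1". Section 11.441 (RECIST 1.1) has the same rule: "evaluation at evaluation times specified in Section 11.1".

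Section 11.33: "A subsequent scan must be obtained a minimum of 4 weeks following initial documentation of an objective status" of response. A note adds: "Once patient has had SD for" at least 6 months, "scanning can be reduced to every 3 months".

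**The concern.** Two imaging schedules are in force, and no text ranks them. A site that follows the calendar breaks Sections 11.431 and 11.441; a site that follows Section 11.1 departs from the calendar.

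The scans determine three things:

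- **The phase II primary endpoint.** Section 16.112 names confirmed ORR by RECIST. A short response that falls between sparse scans can be missed.
- **Progression dates.** Section 16.3 runs PFS to the date of progression, and duration of response is a secondary goal (Section 2.23). Later scans give later dates, and discretion over the interval lets those dates differ between patients for reasons unrelated to their disease.
- **Stopping treatment.** Under Section 13.2, irPD ends treatment. A patient whose progression shows only on imaging stays on the regimen longer under the calendar.

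**Working it through.** **1. Can the texts be reconciled?**

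- Section 11.33 relaxes scanning only after at least 6 months of stable disease. Footnote 5 starts after Cycle 4 whatever the response status, and allows 16 weeks.
- Section 11.33 does not name CR or PR. For responders the conflict can therefore last through the 2 years of treatment in Sections 13.4 and 13.5.
- A single mark under Cycles 4-8 could by itself fit scans at Cycles 4, 6 and 8, but footnote 5 rules that out.

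The calendar omits the 4-week confirmation scan but does not contradict it.

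**2. Scan times.** The Schema gives Cycle 1 = 14 days and later cycles = 21 days. Counted from C1D1, Day 1 of Cycles 2, 3, 4, 5, 6, 7, 8, 9 and 10 falls at weeks 2, 5, 8, 11, 14, 17, 20, 23 and 26.

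- 6-weekly from C1D1: weeks 6, 12, 18, 24. Each is 7 days from the nearest Day 1, outside the calendar's 3-day window.
- 6-weekly from C2D1: weeks 8, 14, 20, 26, which are C4D1, C6D1, C8D1 and C10D1.
- Calendar with a scan at Cycle 4: first scan at week 8 (C4D1) or week 11 (end of Cycle 4), then every 12 or 16 weeks.
- Calendar read literally, with the first scan one interval after Cycle 4: 8 + 12 = week 20 up to 11 + 16 = week 27.

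Scans by week 24: Section 11.1 gives 4 (from C1D1) or 3 (from C2D1). The calendar gives 1-2, or 0-1 read literally. By week 52, for a patient in CR or PR, the counts are 8 against 3-4, or 2-3 read literally. The calendar interval is 12/6 = 2.0 to 16/6 = 2.7 times the Section 11.1 interval.

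**3. Delay in dating imaging-detected progression.** Assumption: time to progression is exponential with median m weeks, m = 8 to 24 (the protocol gives no PFS assumption). Let S(t) = 2^(-t/m). With first scan f and interval h,

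mean delay = f + h·S(f)/(1 − S(h)) − m/ln 2.

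Example, m = 8. Calendar 8, 20, 32, …: 8 + 12 × 0.500/0.646 − 11.54 = 5.74. 6-weekly from C2D1: 8 + 6 × 0.500/0.405 − 11.54 = 3.86. Excess: 1.88 weeks.

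For the Section 11.33 bound, every patient moves to a 13-week interval after the last 6-weekly scan by week 26. The same sum is then taken interval by interval (each interval's length times S at its start).

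| Scan weeks | m = 8 | 12 | 16 | 24 |
|---|---|---|---|---|
| 6-weekly from C1D1 | 3.26 | 3.17 | 3.13 | 3.09 |
| 6-weekly from C2D1 | 3.86 | 3.59 | 3.45 | 3.31 |
| C1D1, all relax (24, 37, …) | 3.81 | 4.21 | 4.54 | 5.00 |
| C2D1, all relax (26, 39, …) | 4.32 | 4.51 | 4.74 | 5.11 |
| Calendar 8, 20, … | 5.74 | 5.81 | 5.85 | 5.89 |
| Calendar 8, 24, … | 7.13 | 7.40 | 7.54 | 7.69 |
| Calendar 11, 23, … | 6.62 | 6.40 | 6.30 | 6.19 |
| Calendar 11, 27, … | 7.68 | 7.74 | 7.79 | 7.85 |
| Literal 20, 32, … | 11.74 | 10.25 | 9.36 | 8.37 |
| Literal 27, 43, … | 17.51 | 15.26 | 13.85 | 12.20 |

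Excess with a first calendar scan at week 8 or 11:

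- Nobody relaxes: 5.74 − 3.86 = 1.88 up to 7.85 − 3.09 = 4.76 weeks.
- Everybody relaxes: 5.89 − 5.11 = 0.78 up to 7.68 − 3.81 = 3.87 weeks.

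The literal reading gives more: 8.37 − 3.31, about 5 weeks, up to 17.51 − 3.26, about 14 weeks, if nobody relaxes.

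**4. Confirmed ORR.** First the plan's own figures: continue if more than 1 of 9 respond, promising if more than 5 of 23. The exact binomial calculation gives type I error 0.099 at 15%, power 0.804 at 35% and early stopping 0.599 at 15%. The stated 10%, 80% and 60% reproduce.

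A response counts as confirmed if it is still present 4 weeks after the first scan following onset. Then

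ORR = 0.35 × P(confirmed | calendar) / P(confirmed | 6-weekly).

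Assumptions: 35% is the true rate under 6-weekly scans; the confirmation scan is done; onset is uniform from week 2 to week 12, 18 or 24; the first calendar scan is at week 8 or 11; duration is 15 weeks plus an exponential part, with overall median 24 or 40 weeks. Section 1.3 gives 15 weeks as the shortest duration in its cited pembrolizumab study.

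- 12-weekly: the longest wait is 12 + 4 = 16 weeks, barely above 15. ORR 34.9-35.0%, power 0.80.
- 16-weekly: the longest wait is 16 + 4 = 20 weeks. ORR 32.2-34.6%, power 0.73-0.79.

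**The case against.** The strongest case on the other side accepts the contradiction and disputes its consequences.

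- **Section 11 does not hold everyone to 6-weekly scans indefinitely.** This stands. It is why two ranges are given: no patient relaxing, and all relaxing. Both are bounds, since the note is permissive and does not name CR or PR.
- **PFS is descriptive.** This stands. The trial is single-arm, and Section 16.3 summarises PFS with a Kaplan-Meier curve and no test against a reference. A reader might infer a biased treatment comparison; there is none to bias.
- **Some progression is found without scans.** This stands. Section 11.46 counts symptomatic deterioration as progression, and superficial lesions can be examined at visits. The delays apply to imaging-detected progression only.
- **The primary endpoint may be unaffected.** This stands in part. A reader might infer a marked loss of power. That would need many responses shorter than 15 weeks, which the documents do not support. The calculation also assumes that the 35% alternative was set with 6-weekly scans in mind, which Section 16.112 does not say.
- **Six-weekly is a preference.** This stands only in part. No text formally ranks Section 11.1 above the calendar, but both sets of response criteria point to it. The choice of anchor is open.

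**Conclusion.** The plan is wrong as written. Footnote 5 and Section 11.1 give incompatible imaging schedules for the scans behind the primary endpoint, PFS dating and the irPD stopping decision, and Section 11.33 does not bridge them. That conclusion needs no modelling.

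The size does. Under exponential PFS with medians of 8-24 weeks and a first calendar scan at week 8 or 11, following the calendar adds about 1.9-4.8 weeks on average to the dating of imaging-detected progression if no patient uses the relaxation, and about 0.8-3.9 weeks if all do after about week 26. The literal reading of footnote 5 adds more.

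The effect on confirmed ORR is uncertain. With no response under 15 weeks it is nil at 12-weekly scanning and modest at 16-weekly (power 0.73-0.79 against 0.80). The documents do not support a claim that the calendar undermines the primary analysis. The two-stage sample size is unaffected.

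**What to change.** - Rewrite footnote 5 and the imaging row to match Section 11.1: every 6 weeks, with no physician discretion over the interval.
- State one anchor in both places. C2D1 is a natural choice: scans then fall on C4D1, C6D1, C8D1 and so on, within the existing 3-day window.
- Show in the calendar the confirmation scan at least 4 weeks after first CR or PR.
- Keep the Section 11.33 relaxation for prolonged stable disease, and say whether it also covers CR and PR.

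The cost is an amendment to wording; no scan is added beyond what Section 11 requires. Where the calendar is now followed, patients would have more CT or MRI scans: 1-3 more by week 24 if the calendar's first scan is at week 8 or 11 (3 − 2 to 4 − 1), and for those in CR or PR 4-5 more by week 52 (8 − 4 to 8 − 3). The literal reading raises the upper ends to 4 (4 − 0) and 6 (8 − 2). The imaging row carries no research-funding mark, so under calendar footnote 1 and Section 19.1 these scans count as routine care charged to the patient.

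A separate consistency fix belongs in the same amendment. Footnote 5 bars PET/CT, while Section 11.32 accepts its CT component if diagnostic quality is documented, and Sections 11.431 and 11.441 list PET-CT as a method. One rule should apply throughout.

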#### 7.14 Pembrolizumab

Trial treatment should be administered on Day 1 of each cycle after all procedures/assessments have been completed. Trial treatment may be administered up to 3 days before or after the scheduled Day 1 of each cycle due to administrative reasons.

Pembrolizumab at the fixed dose of 200 mg will be administered as a 30 minute IV infusion once every 3 weeks. Every effort should be made to target infusion timing to be as close to 30 minutes as possible. However, given the variability of infusion pumps from site to site, a window of -5 minutes and +10 minutes is permitted (i.e., infusion time is 30 minutes: -5 min/+10 min).

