## 7.411 Treatment by a local medical doctor is not allowed.

## 7.412 Three patients will be treated at each dose level and observed for a minimum of 21 days after start of pembrolizumab, to assess toxicities, before new patients are treated. Doses will not be escalated in any individual patient. Decisions on when and how to enroll patients at each dose level are described in Section 16.42.

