## 7.413 Investigators are to contact the Study Chair as soon as any dose-limiting toxicity (DLT) occurs.

## 7.42 Definitions of DLT

## 7.421 For this protocol, DLT will be defined as follows for Cycle 2 only:

CTCAE SOC/AE*	Definition (CTCAE Grade)
Blood and lymphatic system disorders	Grade 4
• Febrile neutropenia	
Eye disorders	≥Grade 3
• Blurred vision	
• Flashing lights	
• Floaters	
Eye disorders	Grade 2 lasting >14 consecutive days confirmed by ophthalmic examination Or Grade 3
• Retinopathy	
Eye disorders	Any grade confirmed by ophthalmic examination
• Retinal vascular disorder	

CTCAE SOC/AE*	Definition (CTCAE Grade)
Eye disorders 
 
• Eye disorders, Other specify
 
	Any visual event $\geq$ Grade 3 confirmed by ophthalmic examination
Investigations 
 
• Alanine aminotransferase increased
 
 OR 
 
• Aspartate aminotransferase increased
 
	$\geq$ Grade 3
Investigations 
 
• Blood bilirubin increased
 
	$\geq$ Grade 3
Investigations 
 
• CPK increased
 
	$\geq$ Grade 3 associated with an increase in creatinine $\geq$ 1.5 times patient's baseline (screening) creatinine level
Investigations 
 
• Creatinine increased
 
	$\geq$ Grade 3
Investigations 
 
• Ejection fraction decreased
 
	$\geq$ Grade 3 Or Absolute decrease of LVEF $>$ 10% compared to Baseline and is below the institution's LLN
Investigations 
 
• Electrocardiogram QT corrected interval prolonged
 
	$\geq$ Grade 3 on at least two separate ECGs
Investigations 
 
• Neutrophil count decreased
 
	Grade 4 lasting $>$ 7 consecutive days
Investigations 
 
• Platelet count decreased
 
	Grade 3 with signs of clinically significant bleeding Or Grade 4
Gastrointestinal disorders 
 
• Diarrhea
 
	$\geq$ Grade 3 for $\geq$ 48 hours despite optimal anti-diarrheal therapy Or Grade 4
Gastrointestinal disorders 
 
• Nausea
 
• Vomiting
 
	Grade 3 for $\geq$ 48 hours despite optimal anti-emetic therapy Or Grade 4

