### 16.2 Sample size and accrual rate

For phase I, the study will require 6-12 patients to complete, allowing for 6 patients per dose level and 2 predefined dose levels. In phase II, the study will require 9-26 patients to complete. Therefore, the total sample size for this study is 15-38 patients. At an anticipated accrual rate of 10-12 patients/year, we expect that this trial will need to accrue patients for anywhere from 15 to 32 months.

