16.42 MTD Determination

The phase I portion of this study will utilize a standard cohort of three design. The dose levels to which patients will be assigned in sequential cohorts are described in Section 7.51. The first cohort of three patients will be treated at dose level 0. Decisions on when and how to dose escalate are described below.

16.421 Three patients will be treated at a given dose level combination and observed for one cycle of the combination (Cycle 2) from start of treatment to assess toxicity.

16.422 If DLT is not seen in any of the 3 patients, 3 new patients will be accrued and treated at the next higher dose level. If DLT is seen in 2 or 3 of 3 patients treated at a given dose level, then the next 3 patients will be treated at the next lower dose level, if only 3 patients were enrolled and treated at this lower dose level.

16.423 If DLT is seen in 1 of 3 patients treated at a given dose level, up to 3 additional patients will be enrolled and treated at the same dose level. If DLT is seen in at least one of these additional three patients ( $\geq 2$  of 6), the MTD will have been exceeded and further accrual will cease to this cohort. If dose-limiting toxicity (DLT) is not seen in any of the three additional patients, 3 new patients will be accrued and treated at the next higher dose level.

16.424 After enrolling 6 patients on a specific dose level, if DLT is observed in at least 2 of 6 patients, then the MTD will have been exceeded and defined as the previous dose unless only 3 patients were treated at the lower dose level. In that case, 3 additional patients will be treated at this lower dose level such that a total of 6 patients are treated at the MTD to more fully assess the toxicities associated with the MTD.

16.426 If a patient fails to complete the first combined cycle (Cycle 2) of therapy for reasons other than dose-limiting toxicity defined adverse events, the patient will be regarded as uninformative in regard to the primary study goal (i.e. MTD determination) and will be replaced.

16.427 Operating Characteristics for standard cohort of 3 design: The following table gives the probability of dose escalation at a single dose level as a function of the true probability of DLT at that level using the cohorts of 3 design described above.

True Rate of DLT (%)	Probability of Dose Escalation
10	0.91
20	0.71
30	0.49
40	0.31
50	0.17

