## 16.5 Data & Safety Monitoring

16.51 The principal investigator(s) and the study statistician will review the study at least twice a year to identify accrual, adverse event, and any endpoint problems that might be developing. The Mayo Clinic Cancer Center (MCCC) Data Safety Monitoring Board (DSMB) is responsible for reviewing accrual and safety data for this trial at least twice a year, based on reports provided by the MCCC Statistical Office.

16.52 Adverse Event Stopping Rules:

The stopping rules specified below are based on the knowledge available at study development. We note that the rules may be adjusted in the event of either (1) the study re-opening to accrual or (2) at any time during the conduct of the trial and in consideration of newly acquired information regarding the adverse event profile of the treatments under investigation. The study team may choose to suspend accrual because of unexpected adverse event profiles that have not crossed the specified rules below.

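### A silent LVEF fall that begins after Cycle 2 Day 1 is a Cycle 2 DLT, but no echocardiogram is scheduled that could find it before the DLT window closes

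*Combined protocol and SAP*

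**What the plan says.** - **The DLT.** Section 7.421 states that "DLT will be defined as follows for Cycle 2 only". Its ejection-fraction row has two alternatives: Grade 3 or higher, or an "Absolute decrease of LVEF" of more than 10% from baseline to below the institution's lower limit of normal. The second alternative requires no symptom. The event must be at least possibly related to study medication.
- **The echocardiograms.** Section 4.1, footnote 6: "Echocardiogram will be performed at baseline, on Cycle 2 Day 1, and Cycle 5 Day 1, then every 12 weeks", for patients who stay on binimetinib. The calendar row has no mark at Cycle 3 Day 1.
- **Order on Day 1.** Section 7.14: "Trial treatment should be administered on Day 1 of each cycle after all procedures/assessments have been completed". The Cycle 2 Day 1 echocardiogram therefore reflects binimetinib alone.
- **The cohort decision.** Under Section 7.412, three patients are treated at each level and "observed for a minimum of 21 days after start of pembrolizumab, to assess toxicities, before new patients are treated".
- **What counts.** Section 16.41 uses only events that occur in Cycle 2. Section 16.52 (Phase I) uses only DLTs observed in the second cycle. Its separate all-cycle review is triggered by related events of Grade 4 or higher.
- **Once a fall is found.** Section 8.2 lists the asymptomatic fall as Grade 1-2, holds binimetinib and requires a repeat LVEF within 2 weeks.

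**The concern.** LVEF can be read only by imaging. The first phase I endpoint is the MTD, and the MTD is a count of DLTs. One row of the DLT table can be met by a patient who feels well, yet the calendar places no LVEF reading between the first pembrolizumab dose and the end of that patient's DLT window. A patient whose LVEF falls silently in Cycle 2 would be recorded as DLT-free.

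Other tests tied to DLT rows are placed near the end of the window: the triplicate ECG and the full eye examination (footnote 7) are both at Cycle 3 Day 1. The echocardiogram is not aligned in the same way. Section 15.17 lists decreased ejection fraction and left ventricular dysfunction as common for binimetinib, so the toxicity is anticipated.

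At stake is whether dose level 0, the starting and highest level, is accepted for phase II on an incomplete DLT count.

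**Working it through.** **1. Visit days.** From the Schema, Cycle 1 is 14 days and later cycles are 21 days.
- Cycle 2 Day 1 = 1 + 14 = day 15; Cycle 2 runs over days 15-35.
- Cycle 3 Day 1 = 15 + 21 = day 36.
- Cycle 5 Day 1 = 15 + 3 × 21 = day 78.
- Gap between scheduled echocardiograms: 78 − 15 = 63 days. Time from Cycle 3 Day 1 to the next reading: 78 − 36 = 42 days.
- The ±3-day visit windows do not close the gap: the earliest Cycle 5 echocardiogram is day 75.
- The calendar also marks an echocardiogram 30 days after discontinuation. Counted from day 15, that is day 45 at the earliest, or day 38 with a 7-day window. Either is after Cycle 2.

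**2. Does a late finding count?** A fall first seen on day 78 was not observed in Cycle 2 (16.52) and cannot be dated to it (16.41). It is outside the count under either wording. The all-cycle review does not catch it either, because it needs Grade 4 or higher and 8.2 grades this fall 1-2.

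**3. What is in hand at the cohort decision?** The days above are per patient, and the decision waits for the last patient. Section 16.2 gives the rate: "At an anticipated accrual rate of 10-12 patients/year". Assume even spacing s = 365.25/12 to 365.25/10 = 30.4 to 36.5 days. The decision on n patients falls on day (n − 1)s + 36 from the first patient's start. Patient k has had the Cycle 5 echocardiogram by then if (n − k)s ≥ 42.
- n = 3: day 97-109; 1 of 3 patients has one.
- n = 6: day 188-219; 4 of 6 have one.
- If all three patients enter within 42 days, 0 of 3 have one.

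None of these readings counts as a DLT.

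**4. The plan's own operating characteristics.** P(pass) = (1 − p)³ + 3p(1 − p)⁵. At p = 10, 20, 30, 40 and 50% this gives 0.906, 0.709, 0.494, 0.309 and 0.172, which reproduces the table in 16.427 (0.91, 0.71, 0.49, 0.31, 0.17).

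**5. Illustration of the bias.** The documents give no Cycle 2 rate for silent falls. Assume other DLTs at 10% or 20%, and an independent unseen LVEF DLT rate of 1% or 3%. The true rate is p = 1 − (1 − other)(1 − unseen).

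| Other DLTs | Unseen | True p | P(pass), falls missed | P(pass), falls seen | Overstated by |
|---|---|---|---|---|---|
| 10% | 1% | 0.109 | 0.906 | 0.891 | 0.015 |
| 10% | 3% | 0.127 | 0.906 | 0.859 | 0.048 |
| 20% | 1% | 0.208 | 0.709 | 0.691 | 0.017 |
| 20% | 3% | 0.224 | 0.709 | 0.656 | 0.052 |

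Expected missed events among 6 patients: 6 × 0.01 = 0.06 to 6 × 0.03 = 0.18.

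**6. Effect of moving the echocardiogram.** On-treatment echo days now: 15, 78, 162, 246, 330, 414 and so on. Moved: 15, 36, 120, 204, 288, 372 and so on.
- Found 42 days earlier: silent falls beginning on days 16-36, 79-120, 163-204, 247-288 and 331-372.
- Found 42 days later: those beginning on days 37-78, 121-162, 205-246 and 289-330.
- With uniform onset (an assumption), the mean shift through day 162 is (84 − 63) × 42/147 = 6.0 days later. Through day 330 it is (168 − 147) × 42/315 = 2.8 days later. Through day 372 it is (189 − 168) × 42/357 = 2.5 days earlier.
- Echocardiograms by day 365: 5 either way. By day 730: 9 now (the last on day 666), 10 if moved (the last on day 708).

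**The case against.** **The Cycle 2 Day 1 echocardiogram is on the first day of the window.** This stands and limits the point. A fall already present then is seen that day and repeated within 2 weeks under 8.2. A reader might infer that the calendar cannot observe this DLT at all, and the documents do not support that. Symptoms, the examination, troponin T or the Cycle 3 Day 1 ECG may also prompt an unscheduled echocardiogram. What remains is the fall that begins after Cycle 2 Day 1 with no such signal.

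**The timing has a rationale.** Section 15.15 puts binimetinib at steady state within 15 days, about when the Cycle 2 Day 1 echocardiogram is done. The pembrolizumab list in 15.27 does not name decreased ejection fraction and gives myocarditis as uncommon. This supports a small bias. It does not show that no fall begins in Cycle 2, because the documents give no onset times.

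**The team can act on later findings.** Section 16.52 allows this: "The study team may choose to suspend accrual because of unexpected adverse event profiles that have not crossed the specified rules below". Some Cycle 5 readings may be in hand by the decision (step 3). But the power is discretionary, and none of those readings enters the count.

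**A single reading could be a false DLT.** Section 7.421 asks for two ECGs for QTc but no confirmation for LVEF. This is a fair caution. It concerns the existing criterion, which the fix leaves unchanged.

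**Other DLT rows also depend on unscheduled tests**, such as Grade 4 neutropenia lasting more than 7 days. True, but this point is limited to LVEF.

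**Conclusion.** The mismatch is real and narrow. For a silent LVEF fall that begins after Cycle 2 Day 1, no scheduled test lies within the DLT window, and a fall not detected until day 78 does not count towards the MTD. For such falls the error runs one way: the DLT count can only be too low.

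The bias is probably small and cannot be quantified from the documents. The range of 0.015 to 0.052 rests wholly on assumed rates and independence. The common category in 15.17 (1% to under 10%) is restricted neither to Cycle 2 nor to silent falls.

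A reader might infer two stronger things. One is that patients would be escalated to an unsafe dose. They would not, because level 0 is already the highest; the risk is accepting it on an incomplete count. The other is that the phase I result would be invalid. The documents give no rate that would support this. The change is a worthwhile, inexpensive improvement to the MTD endpoint.

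**What to change.** For phase I patients only:

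1. In footnote 6 and the calendar, keep the baseline and Cycle 2 Day 1 echocardiograms. Move the Cycle 5 Day 1 one to days 33-36, before Cycle 3 Day 1 dosing, then every 12 weeks. Footnote 7 already follows this pattern for the eye examination.
2. Add to 7.421 and 16.42: *An LVEF fall meeting the DLT criterion on the echocardiogram done before Cycle 3 Day 1 dosing counts as a Cycle 2 DLT. The result must be available for every evaluable patient in the cohort before the cohort decision.* The repeat LVEF in 8.2 applies as written.
3. Phase II keeps footnote 6. Because phase I patients at the recommended dose are included in the phase II analysis, describe LVEF data by phase.

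**Cost.** One footnote, one calendar cell and two sentences, for 6-12 patients. No cohort delay is built in, since 21 days of observation after pembrolizumab starts are already required. The number of echocardiograms is 5 either way by day 365, and 10 instead of 9 over 2 years.

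**Downsides.** Silent falls beginning on days 37-78, and in the matching later intervals, are found 42 days later, which delays the binimetinib hold. Others are found 42 days earlier, and no net monitoring benefit is claimed. The gap after the second on-treatment echocardiogram becomes 84 days, which is the protocol's existing maximum. Phase I and phase II schedules differ. If the later detection is unacceptable, adding the end-of-Cycle-2 echocardiogram and keeping Cycle 5 Day 1 also closes the gap, at one extra echocardiogram per phase I patient (6-12 in all).
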